8.2.4.2. Microbiological Response

In the microbiological response analysis set, the number and proportion of patients with each microbiological response will be calculated. In addition, the number and proportion (eradication rate) of patients who fall in “eradication” or “presumed eradication” categories

and the 95% CI of eradication rate will be calculated in the microbiological response analysis set excluding patients with indeterminate response. Similar calculations will be tabulated by diagnosis (including by detailed diagnostic name of anaerobic infection), by maximum number of daily doses, and by the occurrence of central nervous system disorder. The eradication rate can be calculated by the following formula:

Eradication rate (%) = (Number of patients with “eradication” plus “presumed eradication”/ Number of patients in the microbiological analysis set excluding “indeterminate”) × 100.

In addition, the number and proportion (eradication rate) of patients who fall in “eradication” or “presumed eradication” categories and the 95% CI of eradication rate for each pathogenic organism/strain will also be tabulated by diagnosis.

8.2.4.3. Eradication/Persistence of Each Pathogenic Organism/Strain

In the microbiological response analysis set, the number and proportion of microbes that were considered eradicated will be calculated by pathogenic organism/strain detected by the pretreatment microorganism test. The 95% CI of eradication rate will also be calculated, using indeterminate cases subtracted from the denominator. Similar calculations will be tabulated by diagnosis and by maximum number of daily doses. The eradication rate for a specific pathogenic organism/strain can be calculated by the following formula:

Eradication rate for a specific pathogenic organism/strain (%) = (number of pathogenic organism/strain/number of pathogenic organism/strain detected pretreatment except “indeterminate”) × 100.

8.2.4.4. Subgroup Analysis

For each factor specified in Section 5.4, subgroup analysis on clinical response and microbiological response will be performed based on risk ratio and risk difference. Similar calculations will be tabulated by disease category (anaerobic infection, infectious enterocolitis, amebic dysentery).

8.2.4.5. Exploratory Analysis

For rationales for the assessment of clinical response, the number and proportion of patients will be calculated by diagnosis, clinical response (effective/not effective) and for each rationale.

Furthermore, an additional analysis may be performed as necessary. The exploratory analysis will be reported only when results providing an important interpretation are obtained.

9. LISTINGS

The following listings will be prepared.

- Listing of patients

- Listing of patients with adverse events
- Listing of patients with adverse reactions
- Listing of patients with adverse reactions among patients excluded from the safety analysis set
- Listing of patients with adverse reactions among contraindicated patients
- Listing of patients with serious adverse reactions
- Listing of patients with serious adverse events
- Listing of patients with adverse reactions among patients with hepatic dysfunction
- Listing of patients with adverse reactions among patients with renal dysfunction
- Listing of elderly patients with adverse reactions
- Listing of patients with adverse reactions in the safety specification items
- Listing of patients with central nervous system disorder
- Listing of clinical response and microbiological response
- Listing of microbiological test results
- Listing of results for clinical evaluations (body temperature, white blood cells, CRP)
- Listing for Anaemetro exposure
- Listing of patients who received Anaemetro four times a day at least for one day.

[figure not shown]
Furthermore, the following tables to be used as documents for periodic safety report (PSUR) will be prepared:

- Attachment Form 3 (Listing of overview of patients)
- Attachment Form 2 (Listing of occurrence of ADR and infections)
- Attachment Form 10 (Attachment Form 2-2) (Listing of occurrence of serious adverse events)

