7.3.4. Tests

7.3.4.1. Vital sign/laboratory tests

Vital sign/laboratory tests

Record the following vital sign/laboratory parameters before the initiation of treatment with this drug, during the observation period, and at the completion of observation period.

[Vital sign/laboratory parameters] Body temperature, WBC count, and CRP

- Test date

- Test results

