7.3.6. Effectiveness evaluation

(1) Clinical response

The clinical response of this drug should be evaluated comprehensively at the completion of the observation period, and the results should be recorded.

If this drug is administered continuously for more than 8 weeks, the clinical response should be evaluated comprehensively at Week 8.

- Effective
- Not effective
- Indeterminate (the reason should be recorded.)

The assessment criteria shall be as follows:

Table 2. Assessment criteria for [anaerobic infection] / [infectious enterocolitis (including pseudomembranous colitis)]

Assessment	Definition
Effective	Clinical symptoms accompanying the infection observed at the initiation of treatment with this drug has improved at the time of assessment, and treatment with other antibacterial drugs after the time of assessment is determined not necessary.
Not effective	"Effective" criteria are not met.
Indeterminate	Clinical response is difficult to evaluate.

Table 3. Assessment criteria for [amebic dysentery]

Assessment	Definition
Effective	Clinical symptoms accompanying the infection observed at the initiation of treatment with this drug has improved at the time of assessment, and treatment with other antibacterial drugs other than antiamebic agents (paromomycin, etc.) after the time of assessment is determined not necessary.
Not effective	"Effective" criteria are not met.
Indeterminate	Clinical response is difficult to evaluate.

Any clinically problematic finding compared to the initiation of treatment should be recorded in details in the AE column.

(2) Rationale for clinical response assessment

The rationale for the clinical response assessment ("Effective" or "Not effective"), on the disease for which this drug is used, should be recorded.

[Anaerobic infection]

General clinical findings, body temperature, WBC count, CRP level, imaging, and others

[Infectious enterocolitis (including pseudomembranous colitis)]

General clinical findings, Clostridium difficile TOXIN test, frequency of diarrhea, body temperature, abdominal pain, and others

[Amebic dysentery]

General clinical findings, ameba test, frequency of diarrhea, body temperature, abdominal pain, and others

(3) Microbiological response assessment

Microbiological response at the completion of observation period compared to prior to the initiation of treatment with this drug should be assessed, and the results should be recorded.

Table 4. Assessment criteria for microbiological response

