9.4. Definitions of safety events

9.4.1. Adverse events

An AE is any untoward medical occurrence in a patient administered a medicinal product. The event need not necessarily have a causal relationship with this drug treatment or usage. Examples of AEs include but are not limited to the following:

- Abnormal test findings (see below for circumstances in which an abnormal test finding constitutes an AE);
- Clinically significant symptoms and signs;
- Changes in physical examination findings;

- Hypersensitivity;
- Progression/worsening of underlying disease;
- Lack of efficacy;
- Drug abuse;
- Drug dependency.

Additionally, for medicinal products, they may include the signs or symptoms resulting from the following:

- Drug overdose;
- Drug withdrawal;
- Drug misuse;
- Off-label use;
- Drug interactions;
- Extravasation;
- EDP;
- Exposure during breast feeding;
- Medication error;
- Occupational exposure.

Abnormal test findings

The criteria for determining whether an abnormal objective test finding should be reported as an AE are as follows:

- Test result is associated with accompanying symptoms, and/or
- Test result requires additional diagnostic testing or medical/surgical intervention, and/or
- Test result leads to a change in study dosing or discontinuation from the study, significant additional concomitant drug treatment, or other therapy, and/or
- Test result is considered to be an AE by the investigator or Sponsor.

Merely repeating an abnormal test, in the absence of any of the above conditions, does not constitute an AE. Any abnormal test result that is determined to be an error does not require reporting as an AE.

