6. ENDPOINTS AND COVARIATES

6.1. Safety Endpoints

Safety endpoints include:

- Adverse reactions: Adverse events determined to be related to Anaemetro by the physician
- Adverse events: All-causality adverse events
- Serious adverse reactions or events: Adverse reactions or adverse events in which the seriousness was determined to be serious by the physician
- Safety specification items: The following events will be handled as safety specification items:
 - Central nervous system (CNS) disorder: Events that were considered as a central nervous system disorder by the physician and had a check mark on “yes/unknown” in the corresponding AE item of the CRF
 - Peripheral nerve disorders
 - Aseptic meningitis
 - Toxic epidermal necrolysis, oculomucocutaneous syndrome
 - Acute pancreatitis
 - Leukopenia, neutropenia
 - Carcinogenicity

All safety specification items except central nervous system disorder and all events included in safety specifications will be defined according to MedDRA SMQ, System Organ Classes (SOCs), or Preferred Terms (PTs), or classified according to a classification table prepared using observed AEs based on the risk management plan (RMP). Safety specification items are in accordance with the RMP of Anaemetro submitted in January 2017.

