8.2.3.1. Adverse Reactions

- **Adverse reactions**

The number and proportion of patients with adverse reactions will be tabulated by SOC and PT.

- **Serious adverse reactions**

The number and proportion of patients with serious adverse reactions will be tabulated by SOC and PT.

- **Details of adverse reactions**

The number and proportion of patients with adverse reactions will be tabulated by SOC and PT for each of the following items.

- Seriousness [serious, non-serious]
- Expected/unexpected [Expected, unexpected]
- Intervention [discontinuation, temporarily discontinued or dose reduced]
- Outcome [not recovered, recovered with sequela, recovering, resolved/recovered, unknown]

In addition, the number and proportion of patients with adverse reaction that meets all of the following items will be tabulated by SOC and PT:

- The seriousness was considered “non-serious”;
- The intervention was “discontinuation”, “temporarily discontinued”, or “dose reduced”
- The outcome was “not recovered” or “recovered with sequela”.

If the same adverse reaction (the same PT) occurs more than once in the same patient, it will be handled as follows in the tabulation of the number of patients with events:

- Seriousness: If both serious and non-serious events are reported, “serious” will be adopted.
- Expected/unexpected: If both expected and unexpected events are reported, “expected” will be adopted.
- Number of days to onset: The number of days to the first event will be adopted
- Intervention: If multiple types of action are reported, one of discontinuation, temporarily discontinued or dose reduced, or other (none, dose increased), in descending order of precedence, will be adopted.
- Outcome: The outcome of the last occurring event will be used.

- **Safety specification items**

The number and proportion of patients with the following safety specification items will be tabulated.

- Central nervous system disorder
- Peripheral nerve disorders
- Aseptic meningitis
- Toxic epidermal necrolysis, oculomucocutaneous syndrome
- Acute pancreatitis

- Leukopenia, neutropenia
- Carcinogenicity

In addition, the number and proportion of patients who experienced each safety specification item will be tabulated by intervention and outcome, by SOC and PT.

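### Leukopenia is a named safety item counted only from coded adverse events, and no check of the collected WBC values against a lower limit is planned

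*SAP*

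**What the plan says.** **The safety item.** SAP 6.1 names seven safety specification items, one of which is "Leukopenia, neutropenia". Every item except central nervous system disorder is identified through MedDRA groupings or terms, or is "classified according to a classification table prepared using observed AEs based on the risk management plan (RMP"). No laboratory value enters the definition. SAP 8.2.3.1 then states: "The number and proportion of patients with the following safety specification items will be tabulated".

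**The WBC data.** Protocol 7.3.4.1 instructs sites: "Record the following vital sign/laboratory parameters before the initiation of treatment with this drug, during the observation period, and at the completion of observation period". The parameters are "Body temperature, WBC count, and CRP"; no neutrophil or differential count is named. Protocol 7.3.6 gives WBC a role in effectiveness. The grounds that may be recorded for the clinical response rating in anaerobic infection are "General clinical findings, body temperature, WBC count, CRP level, imaging, and others".

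**What is done with the values.** SAP 9 plans "Listing of results for clinical evaluations (body temperature, white blood cells, CRP"). SAP 8.2.3 has no summary of WBC, no shift table and no count below a limit, and SAP 8.2.3.3 (other safety endpoints) is marked as not applicable.

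**When a low value becomes an adverse event.** Protocol 9.4.1 lists four routes: accompanying symptoms; a need for further diagnostic tests or intervention; a change in dosing, discontinuation or added therapy; or "Test result is considered to be an AE by the investigator or Sponsor". Separately, protocol 7.3.6 tells the investigator to enter in the AE column any finding that is clinically problematic relative to the start of treatment.

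**The concern.** The plan must report a proportion for leukopenia, and it holds serial measurements of the quantity that defines leukopenia, yet the two are never connected. Whether a low count enters the proportion depends on someone recognising it as an event.

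The protocol gives sites little prompting to do so. Its section 6.1 names only central nervous system disorder as a safety specification, and that is the only disorder with its own item in the AE record (protocol 7.3.7). In anaerobic infection, WBC is also one of the things a physician may cite for the response rating, so sites have a reason to look at whether it has come down. Nothing in the plan asks anyone to check whether it has come down too far.

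At stake is how a zero or small count in the safety specification table is read. It could be taken as evidence that leukopenia is rare under this drug, when the plan has not looked systematically at the values that could confirm or qualify that.

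**Working it through.** **1. The plan's own figure.** Protocol 7.5.2 and SAP 2.1 say 100 patients give a 95% probability of detecting an adverse reaction with true incidence 3%.

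- P(at least one) = 1 − (1 − 0.03)^100 = 1 − 0.0476 = 95.2%.
- Smallest n for 95%: ln(0.05) / ln(0.97) = 98.4, so 99.

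The figure reproduces. It assumes that every true case is counted.

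**2. Where a low WBC goes.**

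| On-treatment WBC below a lower limit, and… | Recorded as AE? | In the leukopenia proportion? | In the WBC listing? |
|---|---|---|---|
| symptoms, further tests, treatment or dosing change | yes (protocol 9.4.1) | eligible once coded | yes |
| judged clinically problematic by the investigator | yes (protocol 7.3.6) | eligible once coded | yes |
| judged an AE by investigator or Sponsor | yes (protocol 9.4.1) | eligible once coded | yes |
| none of these | no | no | yes |

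Only the last row is a gap. Those patients appear in a listing but in no numerator. Eligible is the right word for the other rows. The table sits under the adverse reactions heading of SAP 8.2.3.1, and SAP 6.1 defines adverse reactions as events the physician judged related. The text does not say outright whether the item table is limited to related events.

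**3. Sensitivity of the detection figure.** The documents do not give the share *s* of true cases that would be recorded as events, nor the incidence of leukopenia. Taking the plan's 3% as the true incidence and *s* as an assumption, P = 1 − (1 − 0.03*s*)^100:

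| Assumed share recorded, *s* | Effective incidence | P(at least one in 100) |
|---|---|---|
| 100% | 3.00% | 95.2% |
| 75% | 2.25% | 89.7% |
| 50% | 1.50% | 77.9% |
| 25% | 0.75% | 52.9% |

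The first row is the case of no loss, and nothing in the documents rules it out.

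**4. What a zero would mean.** Even with complete recording, 0 of 100 has an exact two-sided 95% upper limit of 1 − 0.025^(1/100) = 3.6%. SAP 8.2.3.1 plans number and proportion only for this item, so that limit would not be shown unless it were added.

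**5. What the stored data can support.** Protocol 7.3.7 requests the site reference value only when a laboratory-related AE has been reported, so site-specific limits are not available for all patients and a pre-set limit is needed. There are no exclusion criteria (protocol 7.2.2), and under 15 years is a planned subgroup (SAP 5.4), so a single adult limit may not suit everyone. Neutropenia cannot be checked this way, because no differential count is collected.

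**The case against.** The strongest reply is that ascertainment through adverse events is the protocol's chosen definition, and that it has safeguards. Clinically problematic findings must go into the AE column whatever the response rating; the Sponsor as well as the investigator may declare a test result an event; the Sponsor can query the CRF (protocol 7.6.3.2); and with about 100 patients the WBC listing can be read by eye. Protocol 7.5.2 also warns that this study may not yield enough information on RMP risks, and that these are monitored through routine pharmacovigilance as well.

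Most of this stands, and it narrows the point to the last row of the routing table. It does not close that row. The documents allow Sponsor review of the values but do not plan it, and a listing supplies neither a numerator nor a denominator. Additional exploratory safety analysis under SAP 8.2.3.5 is optional and is reported only if its result is thought important, so an unremarkable WBC result need not appear.

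A reader might infer four stronger things that the documents do not support:

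- **That a falling WBC is read as response.** WBC is one of several possible grounds for the rating, and nothing says a subnormal value counts as success. A fall is also expected as infection resolves, so the issue is values below a limit, not falls as such.
- **That only the investigator's reports count, or that the data are lost.** The Sponsor may also declare an event, and every value is listed.
- **That the reported incidence is too low by some known amount.** No figure in the documents supports this. An all-cause count of low WBC is also a different quantity from an incidence tabulated under adverse reactions, so one does not correct the other.
- **That the sample size is undermined.** The 95% figure concerns adverse reactions in general and is arithmetically right.

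**Conclusion.** The point holds in a limited form. A named safety specification item is counted from coded adverse events alone. WBC is collected at baseline and on treatment, and no systematic comparison with a lower limit is planned. Low values that are asymptomatic, prompt no action and are not judged an event are therefore listed but not counted.

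The size is unknown. The number of such patients may be zero, and the detection probabilities below 95.2% in the sensitivity table rest wholly on the assumed recorded share and on a 3% incidence that the plan does not state for leukopenia. This is a worthwhile and inexpensive improvement in how the item is ascertained. It is not an error in the plan's definition, and it does not affect the primary effectiveness endpoint or the sample size.

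**What to change.** Add to SAP 8.2.3 one descriptive table, kept separate from the adverse-reaction incidence and labelled all-cause:

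- **Population:** safety-set patients with at least one WBC after the start of treatment, with that number shown beside the full safety set.
- **Content:** baseline WBC and lowest on-treatment WBC, and the number and proportion below a lower limit. The Sponsor should fix the limit and give its basis before database release, with age-appropriate values if children are included. The documents supply no limit.
- **Splits:** baseline WBC below or not below the limit (missing baseline shown separately), cross-tabulated with whether a leukopenia/neutropenia AE was recorded.
- **Footnote:** neutropenia rests on AE reports alone, because no differential count is collected.

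Sponsor review of patients with a low value and no AE record, from the listing already planned, is optional. No new site queries are needed for the table itself.

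The cost is one table on data already collected and one decision about the limit. The drawbacks should be stated with it. Low counts may come from the infection or other drugs. Patients without a follow-up WBC drop out of the denominator, and protocol 7.9 already expects some missing chart data. The protocol also sets no testing frequency, so the lowest recorded value depends on how often each patient was tested.

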10. APPENDIX

10.1. Appendix 1: Example of Table and Figure of Risk Ratio of Incidence of Adverse Reactions by Subgroups

| Event name: XXX increased | Category 1 | | Category 2 | | Risk ratio (RR) | |
|---|----------------------|-------|----------------------|-------|-----------------|--------------|
| | Number of patients/N | (%) | Number of patients/N | (%) | RR | 95 %CI |
| Gender (male vs. female) | 18/2220 | (0.8) | 3/1099 | (0.3) | 2.97 | (0.88-10.06) |
| ≥65 years vs. <65 years | 19/2788 | (0.7) | 2/531 | (0.4) | 1.81 | (0.42-7.74) |
| Diagnosis (Disease A vs. Disease B) | 3/221 | (1.4) | 18/3098 | (0.6) | 2.34 | (0.69-7.87) |
| Duration of illness (<1 year vs. ≥1 year) | 9/771 | (1.2) | 7/866 | (0.8) | 1.44 | (0.54-3.86) |
| Drug A Concomitant use (present vs. absent) | 9/798 | (1.1) | 12/2521 | (0.5) | 2.37 | (1.00-5.60) |
| Drug A Prior treatment (present vs. absent) | 1/148 | (0.7) | 20/3171 | (0.6) | 1.07 | (0.14-7.93) |
| Disease B Complications (present vs. absent) | 16/1614 | (1.0) | 5/1703 | (0.3) | 3.38 | (1.24-9.20) |
| Disease B Past medical history (present vs. absent) | 7/674 | (1.0) | 14/2643 | (0.5) | 1.96 | (0.79-4.84) |
| Hepatic dysfunction (present vs. absent) | 0/80 | 0 | 18/2056 | (0.9) | 0 | 0 |
| Renal dysfunction (present vs. absent) | 1/140 | (0.7) | 17/2004 | (0.8) | 0.84 | (0.11-6.28) |

10.2. Appendix 2: Example of Categorizations for Risk Ratio Analysis

Exploratory categorization factors might be added to the set below. If an additional factor is one that categorized by absent or present, “absent” will be chosen as the reference.

| Categorization item | Categories | Reference |
|--|--|---------------------|
| Age | [<65 years, ≥65 years] | <65 years |
| Diagnostic name 1 | [anaerobic infection, infectious enterocolitis] | anaerobic infection |
| Diagnostic name 2 | [anaerobic infection, amebic dysentery] | anaerobic infection |
| Diagnostic name 3 | [anaerobic infection, anaerobic infection plus infectious enterocolitis] | anaerobic infection |
| Hepatic dysfunction | [absent, present] | absent |
| Renal dysfunction | [absent, present] | absent |
| Prior treatment (medication for infection) | [absent, present] | absent |
| Concomitant medications (medication for infection) | [absent, present] | absent |
| Number of daily Anaemetro doses (1) | [1 time, 3 times] | 3 times |
| Number of daily Anaemetro doses (2) | [2 times, 3 times] | 3 times |
| Number of daily Anaemetro doses (3) | [3 times, 4 times] | 3 times |
| Number of daily Anaemetro doses (4) | [3 times, >4 times] | 3 times |
| Dose escalation | [absent, present] | absent |
